4.5 The Control Group

Traditional antenatal care presupposes monthly visits from the start (as early as possible) to week 28, then visits at two-weekly intervals until week 36, followed by weekly intervals until birth or the end of week 42, at which time post-term referral is common for those who have not yet developed spontaneous labour contractions.

Although this timing is not implemented exactly in all study settings, it is close to most of the recommendations and the actual care provided in private practices in the developing world. There would not be major disagreements among obstetricians in identifying this as the "ideal" programme. The contents of each visit may vary according to the location, for example, regarding screening test. In principle, however, the same routine elements are included in each visit. In practical terms, few public clinics in urban areas of developing countries complete this protocol, even for those women who attend early in pregnancy.

During the preparatory stage of the study, a survey was conducted in all clinics for a baseline description of antenatal care procedures and available resources, adapted from a study recently conducted in Europe (Maratos, 1986). This survey included a random sample of antenatal care visits taken at baseline and once more during the study. A simplified form was filled out, including information on crucial elements of content, interventions and use or resources in both the control and intervention clinics. Clinics, randomized to continue with the traditional care, serve as the comparison group. The personnel were informed of the study and its objectives, before randomization and it is expected that the clinics will themselves update their procedures and attempt to follow the recommended (Western type) protocols more closely (Hawthorne effect). As the main factors related to the present organization of prenatal care have not been changed, this improvement may not be totally achieved; however, it is very likely that the control clinics will offer, particularly to those women attending in early pregnancy, a prenatal care programme more efficient than the one in place before the study was initiated.

As long as this improved care is kept within the framework of traditional care, it should not invalidate comparisons. In fact, it will give the study a stronger arguments in support of the new programme by eliminating the reaction that the new programme is similar to or better than the "old" only because the old was very inefficient. Attempts will be made to demonstrate that the new programme is equal to or better than a "good traditional prenatal care" system.

4.6 Treatment allocation

As already discussed, practical considerations (contamination, simplification of organization of trial, large sample size) demand that the principle of randomization by unit is followed rather than by individual pregnant woman. The benefits and feasibility of this design have been demonstrated recently in two trials evaluating perinatal procedures (Grant, 1989; Bullough, 1989).

Therefore, this is a multi-centre, randomized controlled trial with "cluster allocation". The clusters (between 300 to 500 women in each), consist of a series of selected antenatal care clinics. The clusters were stratified by study site (country), clinic size (number of patients) and randomized within each stratum.

Within each stratum, the clinics were allocated to the new programme or to the "control" group according to a pre-set random code which were independently prepared and not revealed to the clinics' staff until all preparations for participation were completed in each site and training was initiated in the intervention clinics. Recruitment and trial registration will be preceded by a pilot phase, during which the rules and procedures of the new package in particular were tested.

4.7 Outcome Variables (end-points)

4.7.1 General principles

Outcome variables can be classified as primary or secondary, process or impact indicators of cost of the intervention and satisfaction and perceived quality of care. A trial should select as its primary outcome variables those that are:

- (a) more affected by the intervention;
- (b) represent an important clinical or health problem;
- (c) can be recorded as objectively as possible or by an independent observer;
- (d) that occur frequently enough to provide sufficient statistical power. The study will have power for this incidence of the event.

Antenatal care is a complex set of activities aimed at reducing maternal mortality by reducing the likelihood that a pregnant woman will experience a serious complication of pregnancy or childbirth, and by improving the maternal and fetal outcomes of women with complications (McCarthy and Maine, 1992). It is clear that maternal mortality is a rare event and that the sample size required would be unrealistic; thus, a series of surrogate measures and a maternal morbidity index should be used.

Antenatal care should also identify a fetus at risk and prevent its death by treating or delivering it. The care can reduce the incidence of severe intrauterine growth retardation and preterm delivery, and by this mechanism further influence intrapartum and neonatal death. However, intrapartum deaths are mostly affected by factors related to labour and delivery and are less likely than fatal or neonatal death to be affected by antenatal care. Antenatal care has little influence in the death of infants with normal birth weight, except, for example, diagnosing breech presentation and acting upon it.

Furthermore, the effect of prenatal care on perinatal mortality in populations with high perinatal mortality is confounded by the proportionally smaller contribution of fetal death. Intrapartum death in such populations represents a much higher proportion of perinatal death due to lack of delivery services and birth trauma. In these populations, low birth weight is also very prevalent, and these infants are likely to be more vulnerable to intrapartum and neonatal events (Kline et al., 1989).

In summary, what is the optimal primary outcome measure for the ANC study?

1. Antenatal care is a complex set of activities designed to maintain health; reduce the occurrence of disease and complications during pregnancy, childbirth and the post-partum period; and to reduce maternal mortality and fetal death. It is clear that if only maternal and fetal death are considered, these are rare events and the sample size required to evaluate the effect of the intervention would be large.
2. Perinatal mortality can be seen as a global indicator of fetal/newborn health.
3. However, perinatal death is related to several etiological factors:
 - (a) congenital malformations;
 - (b) IUGR/pre-term birth;
 - (c) intrapartum complications;
 - (d) neonatal care;
 - (e) maternal diseases;
 - (f) combinations of the above.

4. Antenatal care has little effect on the rate of perinatal death among normal birth weight infants. In the Oxford region from 1984-1987, only 6% of all intrapartum of postpartum deaths were singleton babies > 37 weeks without congenital malformations or evidence of severe infection. In both developed and developing countries, pre-term delivery accounts for 60 to 80% of all perinatal deaths (Rush, 1976).
5. Perinatal death is influenced by the quality of intrapartum and neonatal care which is mainly unrelated to ANC. In a recent review of all perinatal deaths in the Oxford region, only 47% of babies who died were considered to have a complicated antenatal history (Gaffney et al., 1994). Neonatal intensive care units do remarkably well in "rescuing from death" very preterm infants (Johnson A. 1995).
6. Excluding congenital malformation and intra-partum death, it is very unlikely that ANC will influence perinatal mortality without changing the rate of pre-term delivery and IUGR.
7. Although perinatal death is a dramatic event, prematurity, specially very preterm births apart from being the major instigator of neonatal death, is related to neurological handicaps, motor, sensory and cognitive disorders which are recognized to entail family suffering, cost and social implications. The long-term implications of pre-term delivery are very well-documented in the literature.
8. Trials that are expected to have modest improvements or no improvements over a more complex system (as in the ANC) on relatively rare outcomes, can use surrogate measures to these primary outcomes or combined index (e.g. maternal morbidity index, fetal/newborn health index). (Villar et al., 1990).

In the following sections, we will discuss specific maternal and fetal outcomes.

4.7.2 Maternal variables

The degree to which antenatal care may improve different outcomes is not as easily assessed as one might first surmise. Some of the adverse outcomes which dominate the lists of causes of maternal mortality result from dramatic episodes which arise shortly before or during the actual birth. Whether elements of antenatal care can prevent or ameliorate such outcome, is, still a topic under discussion. Some examples which follow may clarify the issue.

Complications arising from preeclampsia and eclampsia, obstructed labour, intra- and post-partum bleeding, as sepsis due to local infection are major causes of maternal death (Royston & Armstrong, 1989). Although eclamptic fits may occur without any clinical antecedent preeclampsia or other warning, cases may be avoided if preeclampsia is diagnosed and the conditions monitored carefully until timely delivery. This may further explain the different eclampsia rates among populations and time periods (Douglas K, 1992), while the preeclampsia incidence is relatively stable across populations. Obstructed labour may in some cases be anticipated through the case history, by maternal height and physical examination in late pregnancy, and appropriate actions for operative delivery taken. Bleeding complications may be reduced through antenatal treatment of preeclampsia (abruptio placentae) and emergencies anticipated by early diagnosis of placenta previa. Pre-existing anemia may worsen the consequences of bleeding.

The primary outcome of the trial in relation to maternal conditions will be the rate of "maternal morbidity indicator index". This is defined as the presence of at least one of the following severe conditions: proteinuric-preeclampsia, eclampsia or severe hypertension

(> 160/110 mm Hg) during pregnancy or within 24 hours of delivery; postpartum anemia < 90 g/l of hemoglobin and severe urinary tract infection/pyelonephritis, defined as requiring antibiotic treatment or hospitalization. The rate of this index has been estimated to be above 10% in all study sites.

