- third stage excessive bleeding
- puerperal sepsis
- gestational diabetes

III.C. Special perinatal (fetal, newborn) complications and events in previous pregnancies (specify and validate as for III.B.):

- twins, higher order multiples
- low birth weight (LBW): < 2500 g, or to be defined
- intrauterine growth retardation (if feasible)
- rhesus-antibody affection (erythroblastosis, hydrops)
- malformed, chromosomally abnormal child
- macrosomia (> 4500 g) newborn
- resuscitation, other treatment of newborn
- perinatal, neonatal, infant death (also: later death).

IV. History of present pregnancy

- IV.A. Date of last menstrual period (LMP). Certainty of dates (by regularity and accuracy of recall, other relevant information).
- IV.B. Habits: smoking/chewing tobacco, alcohol, drugs (frequency, quantity).
- IV.C. Any untoward events (pain, vaginal bleeding of threatened miscarriage, hemorrhage).
- IV.D. History of malaria attacks.

V. Physical examination

- V.A. Weight and height; blood pressure (BP). Chest, heart auscultation, Symphysis to fundus distance (in centimeters). All women.
- V.B. Signs of severe anemia: complexion, fingernails, conjunctiva, oral mucosa, tip of tongue. Shortness of breath. All women.
- V.C. Consider vaginal examination, especially if untoward events are positive (IV.C)

VI. Special tests

- VI.A. Urine: protein, multiple dipstick for bacteriuria.
- VI.B. Blood: syphilis (rapid test) result while waiting in the clinic. If positive: treat.
Hb: only if signs of severe anemia.
Blood type and rhesus.

VII. Assessment and referral

- VII.A. Determine the expected date of delivery based on LMP and all other relevant information. Use 280-day rule (LMP + 280 days). Observe: same women will refer to the date of the first missed period when asked about LMP, which may lead to miscalculation of term by four weeks.
- VII.B. Risk assessment (advice: see IX): Women are classified as eligible for the basic components of the new antenatal package or in need of special care and to be followed at the clinic or hospital (Classifying form, Appendix I).

For the following conditions, if diagnosed, is recommended:

- diabetes: refer, must have continued higher level care
- heart disease: refer
- renal disease: refer
- epilepsy: advice on continued medication
- drug abuse: special care
- signs of severe anaemia and Hb < 70 g/dl: higher iron dose, or refer if shortness of breath
- HIV positive: counsel on risk to offspring; refer

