4.8 Sample Size

4.8.1 Background

Sample size estimates depend on a number of practical and statistical considerations, some of which can only be surmised and several of which are somewhat arbitrary. Factors that influence sample size are:

1. major outcome variables of interest;
2. pre-intervention level of the major end-points, and the variability of the endpoints in the absence of intervention;
3. effect of intervention on the endpoints selected for study;
4. the chance of claiming that an effect intervention has occurred, when in fact, no effect was present: the alpha level corresponding to the statistical test of significance;
5. the chance of failing to detect an effect of intervention, when in fact, an effect was present: $\beta = 1 - \text{power of the test of significance}$;
6. participation rates of both individuals and entire clusters;

Table 6 : Outcomes of the ANC Randomized Controlled Trial

A. PRIMARY OUTCOMES	Question number in Data Collection Form(s)	Rate
Rate of maternal morbidity indicator index ⁽⁺⁾	See individual items	> 10%
Rate of LBW (<2500g)	50	> 10%
B. SECONDARY OUTCOMES		
Incidence of proteinuric ^(*) -pre-eclampsia or eclampsia	27	
Prevalence of post partum anemia (hemoglobin <90g/l) ^(**)	38	
Incidence of severe urinary tract infection/pyelonephritis (requiring antibiotic treatment ^(***) or hospitalization)	28 and hospital admission	
Rate of treated syphilis and any other STDs	31	
Rate of post-partum positive syphilis test ^(***) (among women without treatment during pregnancy)	39	
Rate of incomplete tetanus immunization	21	
Rate of post partum hospital stay ≥ 7 days for maternal complications	41-42	
Rate of IUGR ^(#)		
Rate of preterm delivery (<37 weeks)	52	
Rate of spontaneous & PROM pre-term delivery : <35weeks : 35-36 weeks	36	
Rate of medically indicated pre-term delivery : <35 weeks : 35-36 weeks	36-37	
Rate of breech presentation at birth	48	
Rate of very LBW (<1500 g)	50	
Rate of Apgar score <5 at 5'	53	
Rate of I.C.U. stay > 2 days	55 (c)	
Rate of fetal death	49	
Rate of pre-discharge neonatal death	56	

* Proteinuria of 2.0 g or more in 24h or 2+ or more on qualitative examination (dipstick)

** Requires postpartum blood samples

*** Excluding the antibiotics given to treat asymptomatic bacteriuria

+ Maternal morbidity indicator index: the presence of at least one of the following:

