Using the above values and the value for the intra-class correlation coefficient estimated from the Argentinian data set, as well as other values close to it, Formula 2 of Donner's was implemented for a two-sided test, a level of significance of .05 ($z_\alpha = 1.96$) and a power of 80% ($z_\beta = .842$).

The results are shown in Tables 7a, 7b and 7c. Please note that Table 7c presents sample size calculations for $\beta = 0.10$ or a power of 90%. This is done to evaluate the effect on the sample size of an approach to reduce the risk of false negative results. For example, take the usual objective of showing that the new model of ANC is more effective than the traditional model:

		REALITY	
		Equivalent	Not equivalent
DECISION	Equivalent		β
	Not equivalent	α	

β = Probability of concluding that the two methods are equivalent, when in fact they are not (say = 0.10).

Suppose the true O.R. = 1.18; we observe, say OR = 1.10. If SE (LnOR) is 0.05,

$$x^2 = \frac{\text{LnOR}^2}{\text{SE}^2 (\text{LnOR})} = 3.6 < 3.84$$

If we conclude that “methods are equivalent”, we are making a mistake. We will do so whenever we observe $\text{OR} < 1.11$. We want then that the probability of making this mistake to be $\beta < 0.10$. The implications of this requirement on the sample size are presented in Table 7c.

From these tables we can see that for $\alpha = 0.05$ and $\beta = 0.20$ for an OR 1.18 and four study sites, a total sample size of approximately 16,000 women is needed, distributed in ten clinics of 450 pregnancies per study site (Table 7a). If we have five study sites, eight clinics per site will be needed (Table 7b). However, we would like to have a power of 90% ($\beta = 0.10$); we will need twelve clinics of 450 pregnancies in each of the four study sites for a

Table 7(a): Total number of individuals (N) and number of clusters per stratum per group (n), for P_c ranging from .07 to .13 in four strata $\alpha = 0.05; \beta = 0.20$

ρ	OR	Size of temporal block m_1					
		300		450		600	
		N	n	N	n	N	n
0	1.16*	15040	7	15040	5	15040	4
	1.18**	12016	5	12016	4	12016	3
	1.20	9841	5	9841	3	9841	2
.00065	1.16	17963	8	19430	6	20896	5
	1.18	14352	6	15523	5	16695	4
	1.20	11753	5	12713	4	13672	3
.001	1.16	19537	9	21793	6	24049	5
	1.18	15609	7	17411	5	19214	4
	1.20	12783	6	14259	4	15735	4
.002	1.16	24034	10	28546	8	33058	7
	1.18	19202	8	22807	7	26411	6
	1.20	15725	7	18677	6	21630	5

N is value obtained from formula (2) of Donner (1992).

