5.1.1 Clinical and laboratory activities

The mean working time for antenatal care services was 10.1 hours per week. All ANC clinics were operated by health promotion staff of the district hospitals. These were general practitioner and professional nurses but no specialists in obstetrics and gynecology. Five education and information activities were available in each clinic, Table 8.

Basic ANC activities were carried out for each pregnant woman. A vaginal examination was performed only in high risk cases. External version for breech presentation was not carried out. A formal risk score classification was not available. The screening laboratory tests and interventions that should be offered to all women were hemoglobin, blood test for syphilis, tetanus immunization and iron-folic acid supplementation. Only 3 clinics offered Rhesus antibody tests and none offered Pap smears and UTI screening. Most of the tests and interventions that should be offered to high risk cases were available except iodine supplements, colposcopic examination and alpha-feto protein determination, Table 9.

Laboratory tests for infectious diseases were performed in high risk cases. Test for hepatitis B were performed routinely in 3 clinics. No testing facilities for toxoplasmosis were available even in high risk cases, Table 10.

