5.2.4 Maternal events during pregnancy

There were 59 subjects (0.9%) with hypertensive disorders of pregnancy. Among these, 4 were eclampsia cases, Table 24.

There were 189 (3.0%) subjects experiencing urinary tract infections during pregnancy, 84 subjects required antibiotic treatment and 29 subjects were admitted to the hospital.

Vaginal bleeding was reported by 136 (2.1%) subjects. There were 65, 33 and 38 subjects in the first, second and third trimester respectively.

The prevalence of anemia during pregnancy using WHO criterion (hemoglobin less than 110 g/l) was 25.9% (2643 subjects). There were 296 (4.7%) subjects with severe anemia (hemoglobin less than 90 g/l), Table 25.

Two hundred and sixty eight subjects had sexually transmitted diseases requiring treatment. Among these, 14 (0.2%) had syphilis.

Prelabour rupture of membranes occurred in 327 (5.2%) subjects.

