d) Pre-eclampsia admitted to hospital
e) Eclampsia

29. Urinary tract infection

- 1 = No
2 = Yes, no treatment
3 = Yes, with antibiotic treatment
4 = Yes, with hospital admission

30. Vaginal bleeding during pregnancy

- 1 = No 2 = Yes

- a) First trimester
b) Second trimester
c) Third trimester

31. Lowest haemoglobin value during pregnancy g/l

Grid for lowest haemoglobin value

32. Was the mother treated for any of the following conditions during pregnancy?

- 1 = No 2 = Yes

- a) Trichomoniasis, moniliasis or any other abnormal discharge
b) Syphilis
c) Any other sexually transmitted diseases

33. Was external version for breech or malpresentation attempted?

- 1 = No, cephalic presentation
2 = Breech or malpresentation, no version attempted
3 = Version attempted

34. Prelabour rupture of membranes

- 1 = No 2 = Yes

164

Subject number

Grid for subject number

LABOUR AND DELIVERY

35. At admission in labour, did the mother have any of the following conditions?
1 = No
2 = Yes, noted during antenatal period
3 = Yes, first noted at admission

- a) Pregnancy induced hypertension
b) Pre-eclampsia
c) Severe anaemia (< 70 g/l)
d) Chronic hypertension
e) Uterine height low for gestational age
f) Malpresentation or breech
g) Multiple gestation
h) Pyelonephritis or urinary infection
i) Vaginal bleeding
j) Diabetes mellitus
k) Cardiac disease
l) Chronic respiratory conditions
m) Renal disease
n) Pelvic mass
o) Isoimmunization Rh(-)
p) Other

36. Fetal heart rate present at admission in labour
1 = No 2 = Yes

37. Onset of labour
1 = Spontaneous
2 = Induction (Complete Question 38)
3 = Elective caesarean section

38. Indications for induction of labour
1 = No 2 = Yes

- a) Prelabour rupture of membranes
b) Post-term
c) Intrauterine growth retardation
d) Chronic fetal distress
e) Pre-eclampsia
f) Maternal medical complications
g) Pregnancy complications
h) Isoimmunization Rh(-)

POSTPARTUM INFORMATION

39. Lowest haemoglobin value g/l

Grid for haemoglobin value

40. Syphilis test
1 = Negative 2 = Positive

Grid for syphilis test

41. a) Maternal death
1 = No 2 = Yes
b) If Yes, cause of death

Grid for maternal death

ICD-10 code

42. Date of mother's discharge from hospital or death

Grid for date of discharge

NEONATAL OUTCOME

43. Date of delivery or abortion

Grid for date of delivery

44. Time of delivery

Grid for time of delivery

45. Total number of fetuses

Grid for total number of fetuses

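### The primary maternal index counts any antibiotic-treated urinary infection, its secondary-outcome twin excludes treated asymptomatic bacteriuria, and the summary form cannot tell them apart; where control clinics do not screen, this can bias the index against the new model

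*Protocol*

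**What the plan says.** The index is a primary outcome. Section 4.7.2 gives its urinary component as "severe urinary tract infection/pyelonephritis, defined as requiring antibiotic treatment or hospitalization". The Executive Summary note, the index footnote to Table 6 and the index footnote in Appendix III (Table VI) define that component in the same way, without exception.

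Table 6 (printed within 4.8.1) also lists severe urinary infection as a secondary outcome. There the antibiotic criterion carries the footnote "Excluding the antibiotics given to treat asymptomatic bacteriuria". The footnote marker stands only on secondary-outcome rows. In the question-number column, the row for the index refers the reader to the component items and does not say whether the footnote comes with them.

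The summary form (Appendix I, question 29) offers four codes: no infection, infection untreated, "3 = Yes, with antibiotic treatment", and infection with hospital admission. Table 6 cites question 28 for this item; on the form it is question 29.

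For the new programme, the first-visit tests in section 4.4.2 include "Urine: protein, multiple dipstick for bacteriuria", and Table 3 marks this urine test for all women. The second-visit content assumes that bacteriuria found at the first visit may have been treated. For the comparison, section 5.1.1 reports of the 12 Khon Kaen clinics before randomisation that "none offered Pap smears and UTI screening".

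**The concern.** Finding and treating bacteriuria is an activity of one arm's programme. Table 2 lists it as a benefit because it should lower the number of overt infections. Under the unqualified definition, a woman treated after a positive screen and coded as antibiotic-treated infection enters the index as a case of severe morbidity. A similar woman in a control clinic that does not screen enters only if she develops overt infection. Within the urinary component, prevention can shrink this imbalance but cannot reverse it.

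Section 4.8.1 names the index as one of two outcomes that the new programme must be shown not to increase. Section 4.2.4 sends a rise of more than 25% in any primary outcome to the monitoring committee. An artefact of ascertainment could therefore count against the programme or hide a real benefit.

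**Working it through.** **1. What the Khon Kaen figures show.** Section 5.2.4: "84 subjects required antibiotic treatment and 29 subjects were admitted to the hospital". 84 + 29 = 113, and 113/6,354 = 1.8%, which is the severe urinary infection figure in the Executive Summary. Nothing coded as treated was taken out.

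The reported index is 8.3%. On the 6,354 women of Tables 24 and 25 that is 0.083 × 6,354 ≈ 527; the smallest count that rounds to 8.3% is 525. Without antibiotic-only infections, and with no overlap between components, the reported counts give:

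- severe postpartum anaemia 403 + pre-eclampsia or eclampsia 25 (9 + 12 + 4, Table 24) + admitted infection 29 = 457 (7.2%);
- the same with all 59 hypertensive disorders = 491 (7.7%).

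So on these counts at least 525 − 491 = 34 of the 84 antibiotic-only cases are in the index, or 525 − 457 = 68 if only pre-eclampsia and eclampsia count. Overlap would raise these minimums. Hypertension first noted in labour is not in Table 24 and would lower them. The upper bound is 84/527 = 16% of the index.

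**2. The plan's own sample size.** Inputs from 4.8.2: "implemented for a two-sided test, a level of significance of .05"; power ("we would like to have a power of 90" per cent); control rates 0.07, 0.09, 0.11 and 0.13; odds ratio 1.18; clusters of 450; intracluster correlation 0.00065 as printed.

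Inflation: 1 + 449 × 0.00065 = 1.292. I used a stratified Mantel-Haenszel size with equal strata and 1:1 arms, N = (1.96√U + 1.2816√V)²/W². With t = ¼ per stratum:

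- U = ¼ Σ t × 1.292 × p̄(1 − p̄) = 0.03091
- V = ¼ Σ t × 1.292 × ½[pc(1 − pc) + pt(1 − pt)] = 0.03088
- W = ¼ Σ t(pt − pc) = 0.003953

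This gives N = 20,773, against 20,780 in Table 7c.

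**3. What a small ascertainment difference does at that size.** Let b be the share of new-arm women, otherwise outside the index, who enter it only through treated screen-detected bacteriuria. The documents give no value, so b is an assumption. With no true effect and index rate p = 10%, the new-arm rate is p₂ = p + (1 − p)b. The effective number per arm is 10,390/1.292 ≈ 8,043.

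Example, b = 1%: p₂ = 0.10 + 0.90 × 0.01 = 0.109. Odds ratio = (0.109/0.891)/(0.10/0.90) = 1.10. Null standard error = √(2 × 0.1045 × 0.8955/8,043) = 0.00482, so the critical difference is 1.96 × 0.00482 = 0.00945. The chance of exceeding it when the expected difference is 0.009 is about 46%.

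| b | New-arm index | Odds ratio | Chance of rejecting |
|---|---|---|---|
| 0 | 10.0% | 1.00 | 5% |
| 0.25% | 10.2% | 1.03 | 8% |
| 0.5% | 10.5% | 1.05 | 16% |
| 1% | 10.9% | 1.10 | 46% |
| 1.5% | 11.4% | 1.15 | 79% |
| 1.78% | 11.6% | 1.18 | 90% |

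Two markers follow. A 25% relative rise needs b = 0.025/0.90 = 2.8%. A true benefit of odds ratio 1/1.18 (10% falling to 8.61%) is cancelled at b = (0.10 − 0.0861)/(1 − 0.0861) = 1.5%.

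**4. If only Khon Kaen were affected.** It contributes 6,765 of about 20,000 women, or 34%. Averaged over the trial, b = 1% there adds 0.9 × 0.34 ≈ 0.3 points (odds ratio about 1.03), and b = 1.78% adds 1.6 × 0.34 ≈ 0.5 points (about 1.06).

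**The case against.** The protocol does contain the exclusion, on the very component to which Table 6 refers the index. One can fairly read this as a definition that was not harmonised rather than a decision to count bacteriuria. That stands, and it is how the point is put here.

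A reader might infer that only the new arm screens. The documents show this for one site of four. Section 4.5 says that visit content varies by place, including screening tests, and expects control clinics to move closer to the recommended protocols.

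A reader might also infer that the 84 cases are largely bacteriuria or fall mainly in the new arm. The counts are pooled over arms and their nature is not reported, so any split would be invented.

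The coding of treated bacteriuria as antibiotic-treated infection is itself an inference. Training covered every form item and a manual of operation was supplied (the Khon Kaen implementation section), but the manual is not shown. Clerks may have coded such women as having no infection. Nor do the documents say how many screen-positive women are treated.

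Finally, the net direction for the whole index is not established. After the first visit the new programme tests urine protein only in some women, which could lower its recorded pre-eclampsia.

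These points limit the size and certainty of the bias. They do not remove the conflict between the definitions or the form's inability to settle it.

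**Conclusion.** The inconsistency is real and lies in a primary outcome: two treatments of one component, a form that cannot apply the narrower one, and reported figures with no exclusion applied to the coded data. The index can be biased against the new model through its urinary component, provided that control clinics do not screen and that treated bacteriuria is coded as antibiotic-treated infection.

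The documents do not support saying that the index is biased, or by how much. The odds ratios of 1.10 at 1% and 1.18 at about 1.8% assume no true effect, a 10% index, the plan's design effect and all four sites affected; with Khon Kaen alone they shrink to about 1.03 and 1.06. The 16% share of index events is an upper bound. The rates that would matter are nevertheless small enough to justify settling the definition before the arms are compared.

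**What to change.** - Carry the asymptomatic-bacteriuria exclusion into every definition of the index: Executive Summary, 4.7.2, the Table 6 index footnote and Appendix III. Correct the question number in Table 6.
- Add a code to question 29, or a written coding instruction, that identifies treated asymptomatic bacteriuria in both arms. Where forms are already complete, use the clinic record where it can be retrieved; section 4.9.1 keeps record numbers for such queries.
- For data already collected, pre-specify before any comparison of arms a sensitivity analysis of the index that counts urinary infection only when admitted (question 29 = 4), with the other components unchanged. Report antibiotic-treated, non-admitted infection separately by arm. Section 6 says that no comparison has yet been attempted, so there is time.

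The admitted-only version should remain a sensitivity analysis. It drops symptomatic infection treated without admission, and admission is not fully independent of arm because the new programme refers persistent bacteriuria.

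The cost is a somewhat lower event rate and a little extra analysis. In Khon Kaen the sensitivity index would fall from 8.3% to no lower than about (527 − 84)/6,354 = 7.0%.
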